**7. Analysis Subsets**

For all analyses, subjects will be analyzed according to the dose and treatment they received, not the dose and treatment to which they were randomized.

**7.1 Primary Analysis Set**

Since this is an Early Development Study, the Primary Set will be the same as the Safety Analysis Set.

**7.2 Safety Analysis Set**

The safety analysis set will consist of all study subjects who receive at least one dose of AMG 986 or placebo.

### **7.3 Pharmacokinetic (PK) Analysis Set**

The PK analysis set will consist of all study subjects who received AMG 986 for whom at least one PK parameter or endpoint can be reliably estimated.

### **7.4 Pharmacodynamics (PD) Analysis Set**

The PD analysis set will consist of all study subjects who received AMG 986 or placebo for whom at least one echocardiographic parameter can be reliably measured.

### **7.5 Subgroup Analyses**

No subgroup analyses are planned. Data from placebo-treated healthy subjects in each of Parts A and B will be pooled across the cohorts within each part for analysis. Subjects getting IV and oral dosing will be pooled separately **for summary of treatment exposure**. Data for placebo-treated subjects in Part C will not be pooled together.

**The presentation of each summary is detailed out in the respective sections under [section 10](#)**

## **8. Interim Analysis and Early Stopping Guidelines**

No formal interim analysis is planned. However, dose escalation will occur after a Dose Level Review Team (DLRT) makes recommendations relating to early closure/extension or alteration of the study based on ongoing monitoring of the study data (ICH GCP 5.5.2).

All available study data including demographics, IP administration, medical history, concomitant medications, adverse events, ECG's, vital signs, plasma PK and laboratory results will be reviewed. Pharmacokinetic data for other cohorts, if available, may be reviewed at the DLRM's. The DLRM's will be conducted in an unblinded manner and all members of the DLRT will be approved to see the treatment assignments following the appropriate Amgen standard procedure. All cohorts in Part A, Part B and Part C will enroll according to the sequence shown on the Study Design and Treatment Schema above and after review of safety data at the previous dose level and modality, as indicated in the schema.

Based on these emerging safety and tolerability data and upon assessment by the Principal Investigator (PI), Medical Monitor and Global Safety Officer (DLRM members), cohorts may be removed or additional cohorts may be added. Subject numbers within each cohort may also be increased or decreased based on the decision from the DLRM.

## **9. Data Screening and Acceptance**

### **9.1 General Principles**

The objective of the data screening is to assess the quantity, quality, and statistical characteristics of the data relative to the requirements of the planned analyses.

## 9.2 Data Handling and Electronic Transfer of Data

The Amgen Global Study Operations-Data Management (GSO-DM) department will provide all data to be used in the planned analyses. This study will use the RAVE database.

Details of PK and external lab data transfers to the data base are provided in the corresponding study data transfer plans. See details of this section in the Data Management Plan (DMP).

An Analysis Dataset for PK Concentrations (ADPC) will be provided to the appropriate CPMS representative from Global Biostatistical Sciences.

### 9.2.1 Echocardiography Data

Echocardiographic data will be collected, tested for quality, and provided by ICON Imaging, Inc. to GSO-DM according to transfer protocols also described in the Data Management Plan. **Due to concerns regarding quality of echocardiographic data from Parts A and B, an additional echo core lab, Brigham and Women's Hospital Research Imaging Core (BWIC), was added to the study on 12th October 2017. While no clinically meaningful inconsistencies were noted upon review of data from both core labs, the precision of measurements from BWIC was noted to be superior and therefore, measurements from BWIC are reported for Part C in lieu of measurements from ICON Imaging while ICON Imaging measurements are reported for Part A and B.**

## 9.3 Handling of Missing and Incomplete Data

The following imputation for missing or incomplete data will be performed if required:

- Incomplete adverse event and concomitant medication dates missing data will be imputed as described in [Appendix A](#). If imputed dates are used, then they will be identified as such in the final study report.

PK concentrations below the lower limit of quantification will be set to zero.

## 9.4 Detection of Bias

Lack of protocol compliance and the potential for biased statistical analyses will be examined by assessing the incidence of important protocol deviations in each cohort. The clinical study team will identify and document the criteria for important protocol deviations.

---

## 9.5 Outliers

All confirmed outlier data will be included in the analyses presented in this statistical analysis plan unless there is sufficient scientific justification (eg, important protocol deviation leading to invalid data) to exclude them.

PK concentration data will be evaluated for outliers by visual inspection and decisions to re-assay individual samples will be made in accordance with standard CPMS practice. All excluded observations will be detailed by CPMS along with reasons for exclusion, in accordance with standard CPMS practices.

## 9.6 Distributional Characteristics

Where appropriate, the assumptions underlying the proposed statistical methodologies will be assessed. If required data transformations or alternative non-parametric methods of analyses will be utilized.

## 9.7 Validation of Statistical Analyses

Programs will be developed and maintained, and output will be verified in accordance with current risk-based quality control procedures.

Tables, figures, and listings will be produced with validated standard macro programs where standard macros can produce the specified outputs.

The production environment for statistical analyses consists of Amgen-supported versions of statistical analysis software; for example, the SAS System version 9.2 or later.

## 10. Statistical Methods of Analysis

### 10.1 General Principles

The primary analysis will occur after the database lock following last subject last visit.

Descriptive statistics will be provided for selected demographics, adverse events, vital signs, ECG, selected laboratory measurements, and selected echocardiographic measures. Descriptive statistics on continuous data will include means, medians, standard deviations (SD), first and third quartiles and ranges, while categorical data will be summarized using frequency counts and percentages.

**AMG 986 and** Placebo-treated subjects in Part A and Part B will be combined to form composite **AMG 986 and** placebo groups, **respectively** for each Part, **wherever appropriate**. . Placebo-treated subjects in Part C will be separated per cohort (HFReF versus HFpEF). Graphical summaries of the data may also be presented.

When data are summarized by time, the values recorded against the scheduled time points (refer to protocol section 7.1) listed in the protocol will be used.

Unless stated otherwise in this statistical analysis plan, the data analysis will be conducted using subjects in the safety analysis set. For statistical analyses comparing change from baseline, only subjects with both baseline and at least one post-baseline assessment will be included.

## 10.2 Subject Accountability

The number and percent of subjects who were enrolled, randomized, received investigational product, completed investigational product, discontinued from investigational product (including reasons for discontinuing), completed study, discontinued the study (including reasons for discontinuing) will be summarized by **pooled AMG 986 and pooled placebo** treatment groups and **all subjects for part A and part B of the study and by each treatment group for each cohort HFrEF and HFpEF and all subjects for part C** of the study. Key study dates for the first subject enrolled and last subject's end of study will be presented **for all subjects in part A and part B and for all subjects in each cohort HFrEF and HFpEF for part C of the study.**

A subject listing and summary table noting inclusion in each analysis subset will be provided for all subjects enrolled **by pooled AMG 986 and pooled placebo treatment groups and all subjects for part A and part B of the study and by each treatment group for each cohort HFrEF and HFpEF and all subjects for part C of the study.** A subject listing noting duration of investigational product administration, reason for discontinuation of treatment, and reason for discontinuing the study will be provided.

## 10.3 Important Protocol Deviations

Important Protocol Deviations (IPDs) categories are defined by the study team before the first subject's visit and updated during the IPD reviews throughout the study prior to database lock. These definitions of IPD categories, sub-category codes, and descriptions will be used during the course of the study. Eligibility deviations are defined in the protocol. The final IPD list is used to produce the summary of IPDs table and the List of Subjects with IPDs. **The summary of IPDs will be provided by pooled AMG 986 and pooled placebo treatment groups and all subjects for part A and part B of the study and by each treatment group for each cohort HFrEF and HFpEF and all subjects for part C of the study.** In addition, a separate listing of all inclusion and exclusion deviations may be provided.

#### 10.4 Demographic and Baseline Characteristics

Demographic (ie, age, sex, race, ethnicity) and baseline characteristics (ie, height, weight, BMI) will be summarized using descriptive statistics **by pooled AMG 986 and pooled placebo treatment groups and all subjects for part A and part B of the study and by each treatment group for each cohort HFrEF and HFpEF and all subjects for part C of the study.** If multiple races have been reported for a subject, the subject will be categorized as multiple-race.

Demographic and baseline characteristics will be presented and reviewed for each subject. Medical and surgical history will also be presented and reviewed for each subject.

#### 10.5 Safety Analyses (Primary Endpoints)

##### 10.5.1 Adverse Events

The Medical Dictionary for Regulatory Activities (MedDRA) version 19 or later will be used to code all adverse events (AEs) to a system organ class and a preferred term. Subject incidence of all treatment-emergent AEs, serious AEs, AEs leading to withdrawal of investigational product, fatal AEs will be tabulated by system organ class and preferred term in descending order of frequency. All adverse event tables will be summarized **by pooled AMG 986 and pooled placebo treatment groups for part A and part B of the study and by each treatment group for each cohort HFrEF and HFpEF for part C of the study.**

Details of each adverse event will be presented and reviewed for each subject. Listings and/or narratives of any on-study deaths, serious and treatment-emergent adverse events, including early withdrawals due to adverse events, will also be provided should they occur.

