The number and percentage of subjects reporting any treatment-emergent adverse events will be tabulated by system organ class and preferred term, and will be further classified by relationship to treatment. Serious adverse events and clinically significant changes in clinical laboratory test values, ECG, or vital signs will be noted. Both exploratory graphical and model-based PK/PD analyses may be conducted with selected PD markers. Modeling of single-dose PK data obtained in Part A may be used to guide selection of doses and dosing intervals in the multiple-dose segment (Parts B and C).

The sample size for all Parts of the study is based on practical considerations and is consistent with the number of subjects enrolled in similar studies. Approximately 152 healthy subjects (8 subjects per cohort in 19 cohorts for Parts A and B) and up to 40 heart failure patients in Part C are expected to be enrolled. For safety considerations, with up to 144 subjects receiving AMG 986 (114 healthy and 30 patients), there is a 99.94% chance of detecting an adverse event with a true incidence rate of 5% or greater and a 99.99 % chance of detecting a more common adverse event with a true incidence rate of 10%. A rare event with a true incidence rate of 1% will have a chance of 76.48% to being detected with the current sample size.

[figure not shown]
For a full description of statistical analysis methods, please refer to [Section 10](#).

**Sponsor:** Amgen, Inc

Approved

[figure not shown]
Study Design and Treatment Schema

Approved

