## 9.2.2 Adverse Events

### 9.2.2.1 Reporting Procedures for Adverse Events That do not Meet Serious Criteria

Adverse events possibly related to any study procedures/study-activity are reported from signing of the ICF. All other adverse events are reported from the time of randomization (first dose of investigational product). The investigator is responsible for ensuring that all adverse events observed by the investigator or reported by the subject that occur from signing of the ICF or from the time of randomization (after the first dose of IP) through the End of Study are reported using the Event CRF.

The investigator must assign the following adverse event attributes:

- Adverse event diagnosis or syndrome(s), if known (if not known, signs or symptoms),
- Dates of onset and resolution (if resolved),
- Severity [and/or toxicity per protocol],
- Assessment of relatedness to IP (AMG 986 or placebo),
- Assessments of relatedness to any study-mandated activity/procedure and
- Action taken

The adverse event grading scale used will be the Common Terminology Criteria for Adverse Events (CTCAE). The grading scale used in this study is described in [Appendix A](#).

The investigator must assess whether the adverse event is possibly related to the investigational product (AMG 986 or placebo). This relationship is indicated by a “yes” or “no” response to the question: Is there a reasonable possibility that the event may have been caused by the investigational product (AMG 986 or placebo)?

The investigator must assess whether the adverse event is possibly related to any study-mandated activity [eg, administration of investigational product, protocol-required therapies, use of medical device(s) and/or procedure (including any screening procedure(s))]. This relationship is indicated by a “yes” or “no” response to the question: “Is there a reasonable possibility that the event may have been caused by a study activity [eg, administration of investigational product, protocol-required therapies, use of medical device(s)], and/or procedure”?

The investigator is responsible for reviewing laboratory test results and determining whether an abnormal value in an individual study subject represents a clinically significant change from the subject’s baseline values. In general, abnormal laboratory findings without clinical significance (based on the Investigator’s judgment) are not to be

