#### **10.5.2 Primary Endpoints**

##### **10.5.2.1 Safety Endpoints**

###### **10.5.2.1.1 Adverse Events**

All subjects who receive a dose of AMG 986 or placebo will be included in the safety analyses. Subject incidence of all treatment-emergent adverse events will be tabulated by system organ class and preferred term according to the medical dictionary for

regulatory activities (MedDRA) terminology. Tables of events, fatal adverse events, serious adverse events, adverse events leading to withdrawal from investigational product or other protocol-required therapies, and significant treatment emergent adverse events will also be provided if observed.

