## **4. Study Endpoints and Covariates**

### **4.1 Study Endpoints**

#### **4.1.1 Primary Endpoints**

- Subject incidence of treatment-emergent adverse events.
- Subject incidence of clinically significant changes in physical examinations, vital signs, laboratory safety tests, and electrocardiograms (ECGs).

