### 11. Changes From Protocol-specified Analyses

We have redefined some of the analyses to be by “treatment group” instead of by “cohort” to emphasize the role of the placebos. As **decided by the study team post discontinuation of the study, most of the summaries (except exposure to investigational product) are not presented by cohort levels for each treatment group and are provided by pooled AMG 986 and pooled placebo groups.** In other places we use the wording “study cohort” to emphasize the different dose levels.

To restrict the scope of analysis post the discontinuation of the study earlier than planned, following changes were made in the reporting of results from protocol-specified analysis:

- Subject-level data listings will not be presented and reviewed for vital signs (protocol section 10.5.2.1.2) and ECG (protocol section 10.5.2.1.3),
- Summary of maximum change from baseline in QTcF and QTcB and maximum post-baseline values in QTcF and QTcB as stated in protocol section 10.2.5.2.1.3 will not be provided.
- Analysis of pharmacokinetic endpoints as stated in protocol section 10.5.3.1 will not be performed by the CPMS group.
- Analysis of echocardiographic measures as stated in protocol section 10.5.3.2 will not be performed. The analysis is restricted to HFrEF cohort for Part C of the study for selected parameters of left ventricular systolic function including left ventricular ejection fraction, stroke volume by volumetric (MoD) and Doppler assessment (LVOT). The summary will be based on PD analysis set.

Analysis of exploratory endpoints as stated in protocol section 10.5.4 will not be performed

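### SAP 10.5.1 omits, and SAP Section 11 does not declare, the protocol's split of TEAEs by relationship to treatment and its table of significant TEAEs

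*SAP*

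**What the plan says.** - **Endpoint.** SAP 4.1.1 gives the first primary endpoint as "Subject incidence of treatment-emergent adverse events". It carries no qualifier for relatedness or grade.
- **Protocol Synopsis, Statistical Considerations.** TEAEs are to be "tabulated by system organ class and preferred term, and will be further classified by relationship to treatment".
- **Protocol 10.5.2.1.1.** This section tabulates all TEAEs and then adds, if observed, tables of "fatal adverse events, serious adverse events, adverse events leading to withdrawal from investigational product or other protocol-required therapies, and significant treatment emergent adverse events". It does not mention relatedness.
- **SAP 10.5.1.** The tables are those in "Subject incidence of all treatment-emergent AEs, serious AEs, AEs leading to withdrawal of investigational product, fatal AEs will be tabulated by system organ class". For Parts A and B the columns are pooled AMG 986 and pooled placebo. For Part C they are the treatment groups within HFrEF and within HFpEF. The section also keeps subject-level reporting: "Details of each adverse event will be presented and reviewed for each subject". It provides listings and/or narratives for deaths, serious AEs, TEAEs and AE withdrawals.
- **SAP Section 11.** The list of cuts opens with "To restrict the scope of analysis post the discontinuation of the study earlier than planned, following changes were made in the reporting of results". It then covers vital-sign and ECG listings, QTc maxima, PK endpoints, most echocardiography and the exploratory endpoints. A preceding paragraph declares the pooling. Nothing is said about AE relatedness or significant TEAEs.
- **Data collected.** Protocol 9.2.2.1 requires, for every AE, severity, action taken and "Assessment of relatedness to IP (AMG 986 or placebo"). Protocol 7.2.20 grades all AEs by CTCAE version 4.

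**The concern.** The primary objective is safety and tolerability, and the AE tables carry most of the tabulated safety result. That weight grows in this SAP, because the QTc maxima and the vital-sign and ECG listings are withdrawn and the AMG 986 doses are pooled within Part A and within Part B.

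The protocol's own tolerability judgements rest on grade and suspected causality. The cohort stopping rules in Table 8 are worded that way. So is the summary of the first 12 heart failure subjects in protocol 2.4.1, which reports that 4 had TEAEs and that every event was grade 1. The planned final tables could not support a statement of that kind by treatment arm.

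There is also a question of traceability. A reader who relies on Section 11 to learn what was cut would conclude that, apart from pooling, the AE analysis is as the protocol planned.

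**Working it through.** No arithmetic in the plan decides this point. The only AE figures are the detection probabilities in SAP 3.2, and they reproduce from 1 − (1 − p)^n:

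- n = 144, p = 5%: 1 − 0.95^144 = 99.94% (stated 99.94%)
- n = 144, p = 1%: 1 − 0.99^144 = 76.48% (stated 76.48%)
- n = 30, p = 5%: 1 − 0.95^30 = 78.5% (stated 78.5%)

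They concern seeing at least one event of any kind and say nothing about relatedness or grade.

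**Step 1: set the AE analyses side by side.**

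| AE analysis | Protocol synopsis | Protocol 10.5.2.1.1 | SAP 10.5.1 | Declared in SAP 11 |
|---|---|---|---|---|
| All TEAEs by SOC and PT | yes | yes | yes | not needed |
| Serious AEs | to be noted | yes | yes | not needed |
| AEs leading to withdrawal | no | yes | yes | not needed |
| Fatal AEs | no | yes | yes | not needed |
| TEAEs by relationship to treatment | yes | no | no | no |
| Significant TEAEs | no | yes, if observed | no | no |
| TEAEs by CTCAE grade | no | no | no | nothing to declare |
| Dose or infusion rate reduced | no | no | no | nothing to declare |

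**Step 2: count.** The protocol passages together plan 6 AE analyses and the SAP keeps 4, so 6 − 4 = 2 are missing. Section 11 declares 0 of those 2. Of the 4 SAP tables, 0 are split by relatedness and 0 by grade.

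**Step 3: what the tables can and cannot distinguish.** This is a constructed example, not trial data. Take one SAP column, the AMG 986 arm of the HFrEF cohort, with 15 planned subjects. The documents do not give the number finally enrolled. Suppose 3 subjects each have one non-serious event with the same preferred term and none stops treatment.

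| Table | All grade 1, unrelated | All grade 2, related |
|---|---|---|
| All TEAEs | 3/15 = 20.0% | 3/15 = 20.0% |
| Serious, withdrawal, fatal | 0/15 each | 0/15 each |
| Related TEAEs (not planned in the SAP) | 0/15 = 0% | 3/15 = 20.0% |
| Worst grade 2 (not planned in the SAP) | 0/15 = 0% | 3/15 = 20.0% |

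The four planned tables are identical in the two cases. Only the two additional ones separate them.

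**Step 4: are the data there?** Relatedness to IP is a yes/no answer for every AE (protocol 9.2.2.1). An AE that changes severity is recorded once at its worst severity (protocol 9.1.2), so worst grade per subject is a maximum over recorded events.

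**The case against.** **The detailed protocol section does not ask for relatedness.** The synopsis refers the reader to Section 10 for the full methods, 10.5.2.1.1 has no relatedness split, and SAP Section 11 declares its changes mainly by Section 10 numbering. On this item the SAP follows the detailed section. That stands as an explanation, and it shows that the protocol is inconsistent with itself. It does not cancel the synopsis, which 10.5.2.1.1 nowhere withdraws, and it gives no cover for the significant-TEAE table, which is in 10.5.2.1.1.

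**Subject-level AE reporting is kept.** This stands too. A reader might infer that AEs will be reported only as incidence of any grade and any cause. The documents do not support that: serious, fatal and withdrawal tables remain, as do per-subject details and listings and/or narratives, and Section 11 removes listings only for vital signs and ECG. The listing columns are not specified, however, and a listing does not give incidence by arm.

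**Grade and dose reduction.** A reader might infer that these tables were dropped without notice. They were not, because no protocol passage plans them; a grade table would be an improvement. Dose reduction is partly visible in the exposure table (SAP 10.5.6), through number of doses, cumulative dose and average dose, for Parts B and C only.

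**The stopping rules do not depend on final tables.** This is correct. An unblinded dose level review applies them during the study. They show which attributes the sponsor treats as informative, not that safety oversight is impaired.

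**The interim 4 of 12.** It is tempting to use this figure as the example of lost information. It combines AMG 986 with placebo, and the text does not divide it by heart failure type. The SAP tabulates by arm within each type, so no planned table would show it.

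**Abbreviated report.** Early discontinuation can justify cutting analyses. It does not explain leaving two cuts out of the section that records them.

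**Conclusion.** The point holds in a limited form. Two protocol-stated AE analyses, the classification by relationship (synopsis) and the significant-TEAE table (10.5.2.1.1), are missing from SAP 10.5.1 and undeclared in Section 11, and the two protocol passages disagree on relatedness. As a result, 0 of 4 planned AE tables gives incidence by relatedness or grade.

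The primary endpoint as defined is still reported, so this does not amount to a failure to analyse it. What is lost is a by-arm summary of related and graded events, on a trial whose tolerability judgements use both. The change should be made. It affects how the safety result can be read, not the TEAE incidence itself.

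The conclusion rests on two assumptions: that the tables named in SAP 10.5.1 are the full set, and that the synopsis wording still binds because nothing in the protocol withdraws it.

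**What to change.** 1. In SAP 10.5.1, add treatment-related TEAEs by system organ class and preferred term, in the columns already used for the other AE tables.
2. Add TEAEs by worst CTCAE grade in the same columns. This goes beyond the protocol and should be labelled as an addition.
3. Restore the table of significant TEAEs with a definition of *significant*, which protocol 10.5.2.1.1 does not give, or state in Section 11 that it is dropped and why.
4. Note in Section 11 that the synopsis and protocol 10.5.2.1.1 differ on relatedness and which one the SAP follows. If relatedness is not to be tabulated, declare that there with the reason.
5. Optional: a table of AEs followed by dose or rate reduction, interruption or withholding. The documents do not show the response options for action taken, so feasibility must be checked. Protocol 6.2.1.3.3 also allows a rate reduction on a vital-sign change without a recorded AE, so such a table could miss cases.

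Items 1 to 4 cost two or three standard tables and a short SAP paragraph. Relatedness and severity are already recorded for every AE, so no new data are needed. The drawback is a slightly longer abbreviated report.

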### 10.5.5 Electrocardiogram (ECG)

Summaries of all ECG parameters and changes from baseline over time will be provided by **pooled AMG 986 and pooled placebo treatment groups for part A and part B of the study and by each treatment group for each cohort HFrEF and HFpEF for part C of the study**. Baseline will be defined as mentioned in [section 6](#). The analysis of Fridericia's (QTcF) QT correction and Bazett's (QTcB) QT correction will be performed for subjects in Part A and Part B using the derived results as specified in [section 6](#).

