#### 10.7 Exploratory Endpoints Analyses

Exploratory endpoints will not be analyzed with the restricted scope of analysis post the discontinuation of the study earlier than planned. However, bio-marker group will provide the mean plots by treatment group and a listing for NT-pro BNP data for HFrEF cohort for Part C of the study.

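### SAP v3.0 tabulates Part A and B safety only as pooled AMG 986 versus pooled placebo, so no committed vital-sign or ECG output shows a relation to dose in healthy subjects

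*SAP*

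**What the plan says.** SAP 10.5.1 summarises all AE tables "by pooled AMG 986 and pooled placebo treatment groups for part A and part B of the study". SAP 10.5.2 (selected chemistry and hematology) and 10.5.3 (vital signs) use the same grouping, and 10.5.5 gives ECG summaries by "pooled AMG 986 and pooled placebo treatment groups for part A and part B of the study". SAP 10.1 forms these composite groups per Part.

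SAP 11 explains that, after early discontinuation, "most of the summaries (except exposure to investigational product) are not presented by cohort levels for each treatment group". It also removes two outputs that could have carried dose information. One is the listings: "Subject-level data listings will not be presented and reviewed for vital signs (protocol section 10.5.2.1.2) and ECG (protocol section 10.5.2.1.3"). The other is the "Summary of maximum change from baseline in QTcF and QTcB and maximum post-baseline values in QTcF and QTcB". SAP 10.7 adds: "Exploratory endpoints will not be analyzed with the restricted scope of analysis post the discontinuation of the study earlier than planned". That removes the exposure-QTc analysis.

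On route, SAP 7.5 says "Subjects getting IV and oral dosing will be pooled separately", but the same sentence limits this to the summary of treatment exposure. On the rows of tables by time, SAP 10.1 says "When data are summarized by time, the values recorded against the scheduled time points" in the protocol schedule are used.

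The protocol planned otherwise. Its synopsis (Statistical Considerations) describes selected safety data by cohort, analyses each Part and route separately, and combines only placebo. Protocol 10.5.2.1.2 puts vital signs by cohort within Part, and 10.5.2.1.4 puts laboratory values by cohort. The AE and ECG sections name no grouping of their own, so the synopsis governs them. Protocol 10.5.1 allows IV and oral results to be reviewed together in some cases, in addition to separately.

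**The concern.** In an ascending-dose study the main safety question is whether findings increase with dose. A column that averages 5 mg with 650 mg, and a one-hour 0.5 mg infusion with a 24-hour infusion totalling 420 mg, cannot answer it. An effect confined to the top doses can look like placebo in the primary safety tables. Blood pressure change is a potential risk named in protocol 2.4.1, so vital signs matter here.

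For AEs, some dose information may survive, because SAP 10.5.1 keeps per-subject details, although it does not say that cohort will be shown. For Part A and B vital signs and ECG there is no comparable fallback. The exposure-response plots that remain (SAP 10.6.1) cover only stroke volume and ejection fraction, and SAP 10.1 makes other graphs optional. Part C does not fill the gap: its subjects are heart failure patients, its doses (10, 30, 100 mg) are tied to week of treatment, and protocol 10.5.2.1.3 says its single ECGs are not meant for assessing a QTc effect.

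**Working it through.** **Inputs.** Six active and two placebo subjects per healthy cohort (protocol 5.1); 11 cohorts in Part A and 8 in Part B (SAP 3.2; SAP 3.1 says 6 for Part B, but only 8 fits the stated 48 active subjects). ECG times come from protocol Tables 9 to 13.

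**The plan's own figures.** Active subjects: 11 × 6 = 66 and 8 × 6 = 48. The chance of at least one AE at 5% incidence is 1 − 0.95^n: 96.6% for n = 66 and 91.5% for n = 48, as SAP 3.2 states.

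**Dilution.** An effect in k six-subject cohorts reads as effect × 6k/n. The effect sizes below are assumptions.

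- 20 ms in one cohort: 20 × 6/66 = 1.8 ms (Part A); 20 × 6/48 = 2.5 ms (Part B).
- 20 ms in three cohorts: 20 × 18/66 = 5.5 ms; 20 × 18/48 = 7.5 ms. Three is plausible for a peak-driven effect: in protocol Table 3, oral Cmax is 12,200, 16,200 and 18,400 ng/mL at 200, 400 and 650 mg, a 1.5-fold spread.
- An AE in 3 of 6 subjects in one cohort: 3/66 = 4.5%; 3/48 = 6.3%; by cohort, 50%.

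Protocol 2.4.1 reports 116 healthy subjects treated, two more than planned, with no split by Part. If both fall in one Part, outside the affected cohort, the one-cohort figures are 20 × 6/68 = 1.8 ms and 3/68 = 4.4%, or 20 × 6/50 = 2.4 ms and 3/50 = 6.0%.

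**Who stands behind each ECG row.** If rows follow nominal time, the pooled active group changes with the schedule. Reading for an assumed 20 ms in one contributing cohort:

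| Part | Post-dose times (h) | Cohorts measured | n active | Reading (ms) |
|---|---|---|---|---|
| A | 0.5, 1, 2, 6, 12, 24, 48 | all | 66 | 1.8 |
| A | 4 | IV 1-2, oral | 48 | 2.5 |
| A | 1.5 | all IV | 30 | 4.0 |
| A | 24.5, 25, 26, 29, 36, 72 | IV 3-5 | 18 | 6.7 |
| B | 0.5, 1, 2, 6, 12, 24, 144 | all | 48 | 2.5 |
| B | 4, 144.5, 145, 146, 148, 150, 156, 168, 192 | oral | 36 | 3.3 |
| B | 1.5, 48, 72, 96, 96.5, 97, 98, 101, 108, 120 | IV | 12 | 10 |

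An effect in one oral cohort therefore reads 1.8 to 2.5 ms (Part A) or 2.5 to 3.3 ms (Part B) wherever oral subjects are measured. An effect in one IV cohort could read up to 6.7 ms (Part A, IV 3-5) or 10 ms (Part B).

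**Search for a remaining dose display.** One pooled row reduces to a single cohort: Part A vital signs at 144 h, taken only in IV Cohort 5 (Table 10, footnote T). That is 144 − 24 = 120 h after the infusion ends, with no other dose beside it, so it shows no relation to dose.

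**The case against.** SAP v3.0 serves an abbreviated report after early discontinuation, and SAP 11 openly lists what was cut. The study is descriptive, the stated detection chances are for Part totals rather than cohorts, and six subjects give only a 26.5% chance (1 − 0.95^6) of showing an AE of 5% incidence. Quartiles and ranges stay in the tables, so extreme values remain visible, though without a dose label. Vital-sign or ECG changes reported as AEs stay in the per-subject details. The protocol's Amendment 7 rationale reports no evidence of a QTc effect in Parts A and B. All of this is fair. It limits how much cohort tables could show, but it does not replace them, and a mean shift that nobody records as an AE would still have no dose attached.

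Several stronger readings are tempting and not supported:

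- *That dose effects were hidden from escalation decisions.* Protocol 3.1 and 6.2.1.3.1 provide for unblinded dose-level review of each cohort.
- *That the change is undisclosed.* The loss of cohort tables is disclosed. What SAP 11 omits is that routes are combined, which has to be worked out from SAP 7.5 and 10.1.
- *That any effect varies about fourfold between rows.* That holds only for an effect in an IV cohort (IV 3-5 in Part A: 6.7/1.8 = 3.7; Part B: 10/2.5 = 4). For an oral cohort it is 66/48 = 1.4 or 48/36 = 1.3.
- *That the Part B 144 h ECG row certainly mixes treatment phases.* The schedules put IV subjects 48 h past their infusion and oral subjects just before dose 7, but whether both share a row is inferred; the documents show no table layout.

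**Conclusion.** The point holds. The Part A and B safety tables cannot show dose dependence, and for vital signs and ECG no other committed output does so in healthy subjects. This departs from the by-cohort, by-route plan in the protocol and weakens the report on its own primary objective. Conduct of the study is unaffected.

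One cohort is 6/66 = 9.1% of the Part A active column and 6/48 = 12.5% of the Part B column, so a single-cohort effect shrinks about 11-fold or 8-fold in rows where every cohort contributes, and by a third of that if three cohorts respond alike. The group sizes are planned numbers, the effects are illustrations, and the row-by-row figures hold only if tables use nominal time across routes. Nothing here suggests that a safety signal exists. The change is worth making before the report is produced.

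**What to change.** In SAP 10.5.1 to 10.5.3 and 10.5.5, tabulate Parts A and B by dose cohort within route, keep pooled AMG 986 as a total column, and print n at each time point. Keep placebo pooled either by Part (protocol 10.1.3 and 10.5.1) or by Part and route (synopsis), and record the choice in SAP 11. Pooling by route leaves 2 × 2 = 4 placebo subjects for Part B IV.

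If cohort tables must stay out of scope, the minimum is to restore the Part A and B vital-sign and ECG listings with cohort shown, show cohort on the AE listings, and state in SAP 11 that IV and oral are combined.

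The cost is SAP wording and a rerun of the same tables by cohort. Protocol 2.4.1 describes all 19 healthy cohorts as fully implemented by 01 June 2018, so no new data are needed. The tables become longer, and with about six active subjects per cohort they are descriptive only.
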